### 7.2 Analysis Populations

#### 7.2.1 Full Analysis Population

Patients completing their run-in and at least one follow-up visit make up the full analysis population. For purposes of analysis patients who are not randomized are still considered as assigned to “long-term follow up” “treatment” and part of the analysis population. The focus of the model-based analysis though will be on the parameters coding for the effects among the randomized patients. Some will be randomized once, some twice, some not at all, dependent on the PGIC status. Intent to treat is defined as a prospective list of treatment assignments at T2 and T3 conditionally on patients’ all possible longitudinal PGIC status values at those visits. This collection by the PGIC status makes up the patient’s assignment list. Assignments are generated for each recruited patient who completes the run-in (T1 and T2) prospectively. Actual treatments may deviate from the dynamic treatment regimen (when not on the specific patient’s assignment list). The primary analysis will be done under

## Statistical Analysis Plan

the intent-to-treat framework using the treatment assigned to each subject instead of the treatment that each subject may have actually received.

### 7.2.2 Per-protocol Population

The per-protocol population will include all subjects who remain in the study to time T4 and are judged to have been compliant with their assigned treatments. Descriptions of treatment compliance are found in Section 9.5 in Table 4. A sensitivity analysis restricted to the per-protocol population will be done to assess differences between actual vs intended treatment effects.

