3.1 Overview of Study Design

We will conduct a long-term pragmatic trial in a cohort of cLBP patients (see Figure 2 above). The proposed SMART will consist of a 4-week run-in period using an online cognitive-behavioral self-management intervention (PainGuide), followed by two 8-week treatment periods. All participants will be followed for approximately nine months. At baseline (T1), all patients will undergo a comprehensive baseline phenotyping assessment. After receiving PainGuide for 4 weeks, all participants will complete a light phenotyping assessment (T2) and a subset of these patients ($n=160$) will complete an additional deep phenotyping assessment (described in Sections 3.2 and 10). Those who have minimal or modest improvement in their pain ($PGIC\geq 2$) will be randomized to one of the four 8-week long interventions (i.e., MBSR, PT/exercise, acupressure, or duloxetine). Following the first 8-week treatment period, patients will be reassessed (T3) using light only or light plus deep assessments (for the subset of 160) and those who have minimal or modest improvement in their pain ($PGIC\geq 2$) will be re-randomized to receive one of the three treatments they did not

receive in the first treatment period. After the second intervention and three months later, all undergo the light phenotyping follow-up assessment protocol (T4). Lastly, a final assessment will take place at 3 months after the scheduled end of the second 8-week treatment period (T5). There will also be a series of 12 “mini” assessments that take place at 2-week intervals in between the regular assessments (T1-T5). Primary outcome completion date will be defined as the date of the final collection of data for the primary outcome. For this study, this will be the completion of the PROMIS Pain Interference questionnaire at T3. Study completion date will be the date of the T5 study visit.

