## 4.3 Endpoints

The primary study endpoint is the change in the PROMIS (Patient-Reported Outcomes Measurement Information System) pain interference score between the T2 pre-intervention visit and T3 post-intervention visit. The PROMIS pain interference measures the degree to which a patient's pain interferes with the patient's life. The survey questions assess interference in different domains including work around the home, recreational activities, and social activities. A univariate pain interference score is calculated from the respondent's answers. This process is described in Section 9.2.

The study's secondary endpoints consist of the change in the Pain Intensity (PEG) and the Patient Global Impression of Change (PGIC) between the T2 pre-intervention visit and T3 post-intervention visit. The other exploratory PROMIS measures will include a measure of physical functioning, fatigue, sleep disturbances, and cognition. The process of computing each secondary endpoint from survey responses is found in Section 9.2.

Figure 1 Study aims and overview

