## **8.1 Subject Disposition**

A patient will be considered to have reached stage  $t$  after they complete the patient reported outcome forms within the specified stage  $t$  window. A subject will be considered to have dropped out of the study at stage  $t$  if they progressed to the prior stage but fail to complete the patient reported outcome forms within the stage  $t$  window. Whenever possible, the reason for each subject's dropout will be recorded. See Protocol for details concerning the timing of study assessments.

The full analysis population consist of all subjects who complete the patient reported outcome forms at stage T2 at the end of the run-in phase. The full analysis population size will be a count of these patients. The per-protocol analysis populations will consist of all patients who remain in the study and are complaint with their treatment assignments during the first and second treatment periods. The per-protocol population sample size will equal the number of patients who complete the study to stage T4 and are compliant with treatment. Treatment compliance is defined in Section 9.5.

Subjects will be recruited into the study over the course of 2.5 years. Target recruitment rates vary by month based on historical recruitment averages at the BPC. On average, the study aims to recruit 10-15 subjects per month.

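### The only per-protocol set requires staying to T4 and complying in both periods, so a per-protocol reading of the T3 endpoint selects on T3 response and on later behaviour

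*SAP*

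**What the plan says.** - **Endpoint.** SAP 4.3 takes as primary the change in PROMIS "pain interference score between the T2 pre-intervention visit and T3 post-intervention visit". Protocol 3.1 agrees when it fixes the primary completion date: "For this study, this will be the completion of the PROMIS Pain Interference questionnaire at T3".
- **Per-protocol set.** SAP 7.2.2: "The per-protocol population will include all subjects who remain in the study to time T4 and are judged to have been compliant". The compliance in question is to each patient's own assignment. SAP 8.1 makes clear that this covers "treatment assignments during the first and second treatment periods", and adds: "The per-protocol population sample size will equal the number of patients who complete the study to stage T4 and are compliant with treatment". No set limited to the first stage is defined.
- **Its purpose.** SAP 7.2.2: "A sensitivity analysis restricted to the per-protocol population will be done to assess differences between actual vs intended treatment effects". SAP 7.2.1 places the primary analysis under intent to treat.
- **Who gets a second treatment.** Under SAP 5.1, only patients with PGIC of 2 or more at T3 are re-randomised; those with PGIC of 1 go to follow-up. SAP 7.2.1 treats non-randomised patients as assigned to long-term follow-up. The compliance table in SAP 8.5 sets no standard for that.
- **The model.** SAP 9.1 and 9.1.1 fit T3 and T4 jointly. T3 is the target and T4 is added for efficiency. If the joint assumptions fail, the analysis falls back to first-stage data alone.

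**The concern.** The T3 score is recorded before the second treatment begins. A patient who complied fully with the first treatment and has a T3 score still leaves the per-protocol set if they drop out before T4 or do not comply with a different, later treatment. Neither event says anything about whether the T3 score reflects the first treatment as actually taken.

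The exclusion also depends on the outcome by design. The second compliance test reaches only patients whose T3 response was short of the top PGIC category, while the best responders face no such test. PGIC from T2 to T3 is itself a secondary endpoint, and SAP 9.1 repeats the Objective 1 analysis for it, so membership of the set is partly fixed by an outcome being analysed.

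At stake is how the sensitivity analysis is read. If its T3 result differs from the intent-to-treat result, the gap could come from first-treatment adherence, which is what the analysis is meant to show, or from selection after T3. The plan gives no way to tell these apart.

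**Working it through.** **1. The plan's nearest figure.** The SAP gives no expected size or power for the per-protocol set. SAP 6.1 states at least 80% power for a correlation of 0.28 with 102 patients per arm, two-sided 5%. By Fisher's z, power = Φ(atanh(r)·√(n−3) − 1.96) = Φ(0.2877 × 9.950 − 1.96) = 81.7%. The stated figure reproduces.

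**2. Share of first-stage compliers dropped.** Inputs, all assumed because the documents give none:
- retention from T3 to T4: a = 0.85 to 0.90;
- second-stage compliance among the re-randomised: c = 0.70 to 0.80;
- PGIC of 1 at T3: p = 0.10 to 0.20, with no second treatment to comply with.

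Taking retention as independent of compliance, and equal in both groups, share kept = a × [p + (1 − p) × c].
- Mild end: 0.90 × (0.20 + 0.80 × 0.80) = 0.90 × 0.84 = 0.756, so 24% dropped.
- Severe end: 0.85 × (0.10 + 0.90 × 0.70) = 0.85 × 0.73 = 0.6205, so 38% dropped.

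If instead everyone lost before T4 would also have counted as a second-stage non-complier, the loss is (1 − p)(1 − c): 0.80 × 0.20 = 16% to 0.90 × 0.30 = 27%.

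**3. Tilt toward responders.** With the same inputs, the PGIC-of-1 share within the set is p / [p + (1 − p)c]. A true 20% becomes 0.20/0.84 = 24% to 0.20/0.76 = 26%. A true 10% becomes 0.10/0.82 = 12% to 0.10/0.73 = 14%. This occurs even when second-stage compliance is unrelated to pain.

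**4. Size and precision.** Assume further that 85% of an arm comply with the first treatment and have a T3 score. A first-stage set then has 0.85 × 102 = 86.7 per arm, with power 75% at r = 0.28 by the formula in step 1. The SAP's set has 86.7 × 0.756 = 65.5 to 86.7 × 0.6205 = 53.8 per arm, with power 62% to 54%.

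**5. Direction of bias.** An illustrative one-arm simulation assumed a true moderator slope of −0.28 SD, PGIC of 1 in 10–20%, a second-stage pass level of 50–90%, and a latent PGIC correlated 0.7 with T3 change.
- With second-stage compliance unrelated to outcome and moderator, mean T3 change in the set still looked 0.01–0.15 SD better than in all patients.
- With compliance or retention depending on T3 outcome, the moderator or both, the shift ran from about 0 to 0.43 SD.
- Over all scenarios the estimated slope ran from −0.23 to −0.35, on both sides of the truth.

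These results show what is possible under the assumptions. They are not estimates for this trial.

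**The case against.** The strongest reply is that the T4 requirement has a purpose. The Objective 1 model is joint: the T4 rows help estimate the same interaction parameters as the T3 rows, so a per-protocol version has reason to ask for second-stage compliance. SAP 7.2.1 defines intent to treat over the two-stage assignment list, and SAP 6 defines the target group by completion of T1 to T4. This stands for the T4 rows and for the embedded-regimen analyses in SAP 11. It does not justify removing T3 rows. It fails altogether for the first-stage-only fallback, where second-treatment compliance would restrict an analysis containing no second-treatment data.

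The second reply is that the role is limited: this is one sensitivity analysis beside an intent-to-treat primary, and SAP 8.3 plans other versions that exclude violators or impute their responses. That also stands and limits the weight of the point. None of those versions supplies a first-stage per-protocol set.

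Three stronger readings are tempting:
- A reader might infer that the primary result is compromised. It is not, because it follows assignment.
- A reader might infer that the per-protocol result is known to be biased, because later dropout and adherence must follow T3 pain. The documents give no evidence on that dependence, and the simulated slope moves either way.
- A reader might multiply retention by compliance for everyone and obtain a loss of 28% (1 − 0.90 × 0.80) to 40% (1 − 0.85 × 0.70). That ignores patients with PGIC of 1 at T3, who have no second treatment.

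**Conclusion.** The point holds as one about a sensitivity analysis. The endpoint is complete at T3, the only per-protocol set is conditioned on T4 and on both treatment periods, and the second compliance test reaches only patients re-randomised because of their T3 response. For T3, the set therefore cannot cleanly separate treatment as taken from treatment as assigned.

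On the assumptions in step 2 of the working, about 24–38% of first-stage compliers would be dropped; the figure is lower if dropout and non-compliance overlap. Neither the size nor the direction of any bias can be derived from the documents, which give no T3 response, second-stage compliance or T4 retention rate. The change should be made before analysis, because redefining the set afterwards would look post hoc.

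**What to change.** Define per-protocol membership by stage in SAP 7.2.2 and 8.1:
- **T3 observation:** included if the T3 outcome is observed and the patient complied with the first assigned treatment.
- **T4 observation:** included only if, in addition, T4 is observed and, where re-randomised, the patient complied with the second treatment.

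Apply the rule row by row in the joint model of SAP 9.1.1. Use the T3 rule alone for the first-stage-only fallback and for any other per-protocol analysis of T3 alone. Keep the current T4 definition for the dynamic-regimen analyses.

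The cost is SAP wording, with no new data or visits. The downside is that T3 and T4 rows in the joint model then come from slightly different sets of patients, and selection into the T4 rows remains; the report should say so.

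Two related repairs belong in the same edit. SAP 7.2.2 and 8.1 send the reader to Section 9.5 for compliance, but the table is in 8.5. Its duloxetine row names a method of assessment without a threshold, so membership in that arm cannot be determined as written.

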### 7.2.3 Safety Population

The safety population includes all patients who enter the study at study period T1. Safety analyses will use the safety population to assess the rate of adverse patient events. Safety analysis will be done based on adverse event rates for the whole safety population regardless of their treatment assignments or actual treatments.

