23.2 Study Governance and Oversight

23.2.1 Data Safety Monitoring Board (DSMB)

The Data and Safety Monitoring Board (DSMB) acts in an independent, advisory capacity to the study sponsor, National Institute of Arthritis and Musculoskeletal and Skin Diseases (NIAMS), to monitor study progress, data quality, and accumulating safety data, in order to alert the Institute regarding any potential safety or other monitoring concerns affecting the conduct of the study. The DSMB is provided access to the study protocol, consent forms, and other pertinent study related documents, in addition to comprehensive reports with study data to aid in the data and safety monitoring for the duration of the study. The board will meet at least semiannually to assess safety and efficacy data from each arm of the study. The board will operate under the rules of an approved charter that will be written and reviewed at the organizational meeting of the DSMB. At this time, each data element that the DSMB needs to assess will be clearly defined. The DSMB will provide its input to the sponsor and communications will be coordinated by the NIAMS Executive Secretary. The responsibilities of the DSMB are described below.

- Review the research protocol, Data and Safety Monitoring Plan (DSMP), and informed consent documents, including all proposed revisions. The Manual of Operating Procedures (MOP), which may contain the sections included above, is also reviewed.
- Evaluate the progress of the study on an ongoing basis, as needed, including periodic assessments of data quality, participant recruitment, accrual and retention, participant risk versus benefit, performance and other factors that can affect the outcome.
- Evaluate safety throughout the course of the study through the routine review of aggregated adverse event safety data, in addition to expedited review of unanticipated problems, serious adverse event reports, and protocol deviations/violations impacting participant safety. The DSMB Safety Officer reviews the documentation provided by the study team and makes recommendations to the NIAMS regarding protection of the participants.

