## 5 Study Methods

### 5.1 General Study Design and Plan

We will conduct a 36-week pragmatic trial in a cohort of cLBP patients (see Figure 1 and Figure 2). The proposed SMART will consist of a 4-week run-in period using an online cognitive-behavioral self-management intervention (PainGuide), followed by two 8-week treatment periods. All participants will be followed for a total of approximately nine months.

At baseline (T1), approximately 500 patients will undergo a comprehensive baseline phenotyping assessment. After receiving PainGuide (access to an online self-management program) for 4 weeks, each participant will complete a light phenotyping assessment (T2) and a subset of these patients (n=160) will complete an additional deep phenotyping assessment. Those who still have significant pain interference ( $\geq 2$  from Patient Global Impression Scale, PGIC) will be randomized to one of the four 8-week long interventions (i.e., Mindfulness-Based Stress Reduction (MBSR), Physical Therapy (PT)/Exercise, Acupressure self-management [eHealth app], or Duloxetine). Participants with a PGIC=1 will not be randomized and continue with long-term follow-up. The PainGuide run-in is designed to provide the lightest “touch” intervention and to help control for regression to the mean. We will use block randomization with random block size of 4 and 8. Approximately 102 patients will be assigned to each treatment group including Physical Therapy/Exercise, MBSR, Acupressure, and Duloxetine treatment groups. For addition details, please see Section 6.3.

Following the first 8-week treatment period, patients will be reassessed (T3) using light only or light plus deep assessments (for the subset of 160) and those still having significant pain interference ( $\geq 2$  from Patient Global Impression Scale [PGIC]) will be re-randomized to receive one of the three treatments they did not receive in the first treatment period. Participants with a PGIC=1 will not be randomized and continue with long-term follow-up. After the second intervention and three months later, all undergo the light phenotyping follow-up assessment protocol (T4). Lastly, a final assessment will take place at 3 months after the scheduled end of the second 8-week treatment period (T5). There will also be a series of interim assessments that take place at 2-week intervals in between the regular assessments (T1-T5).

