## 5.4 Inclusion-Exclusion Criteria and General Study Population

### 5.4.1 Participants

Subjects who are ages 25-70 years and who are being seen at Michigan Medicine will be recruited.

Diversity in race and ethnicity is anticipated. All races and ethnicities will be considered for inclusion in the study. Enrollment will be defined as the number of participants consented and randomized into the 4 treatment arms. This study will enroll 408 participants (up to 102 into each intervention) and it is expected that approximately 500 participants may be consented to meet enrollment. Enrollment will be stopped when this enrollment goal is met.

There will be two sets of inclusion and exclusion criteria. The first set is for enrollment into the research project for all participants. The second set represents additional exclusion criteria that are necessary for the safe and valid conduct of the deep phenotyping protocol (subset n=160).

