## 10 Safety Analyses

Even though no serious side effects are expected from the treatments, in addition to the safeguards in the SMART trial of the Research Project, the Core will monitor safety periodically with 3 interim analyses and one final analysis, using the Fleming design. The analysis will occur after each consecutive recruitment group of another 102 patients has completed their treatments (408 planned patients total under active treatments after drop-out).

Although it is highly unlikely that there will be extensive adverse events related to the study treatment that is any grade 2 or higher because these are all commonly used treatments for cLBP, we have established an alarm procedure. The alarm procedure is designed to give early warning if the rate of any related AEs, grade 2 or reaches 15% or above. The standard rate is assumed to be 10%. We will consider an alarm when more than 21, 31, 41, and 51 patients show adverse events and classify as related events and are a grade 2 or higher at the 3 interim tests and the final analysis, respectively. If the rate of adverse events is indeed at 15% or higher, the suggestion to stop the trial will be generated by this procedure at 253 treated patients or less on average. Errors of both types are set at 5%. A decision that the rate is safe will be suggested after 265 patients on average.

Events that may require the study to be discontinued or participant to be withdrawn from the study are described in the Protocol Section 18.1.6 and Section 22.

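### The SAP specifies no adverse-event rate by treatment: its safety analysis and its only alarm rule pool all participants, although the Protocol has the DSMB look at safety in each arm.

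*SAP*

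**What the plan says.** SAP 7.2.3 defines the population broadly: "The safety population includes all patients who enter the study at study period T1". It then sets the grouping: "Safety analysis will be done based on adverse event rates for the whole safety population regardless of their treatment assignments or actual treatments".

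SAP section 10 adds one formal rule. Looks follow each group of 102 treated patients, 408 in all. An alarm is raised when more than 21, 31, 41 and 51 patients have had a related event of grade 2 or higher. The assumed standard rate is 10%, and the purpose is stated as: "The alarm procedure is designed to give early warning if the rate of any related AEs, grade 2 or reaches 15% or above". The count is not split by treatment. The rest of section 10 covers definitions, management and reporting timelines. No adverse-event table by treatment appears, although SAP section 8 does plan baseline characteristics and outcome missingness by intervention group.

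Protocol 23.2.1 says of the DSMB: "The board will meet at least semiannually to assess safety and efficacy data from each arm of the study". The same section also speaks of reviewing adverse events in aggregate. Protocol section 23 refers to a separate Data Safety Monitoring Plan (DSMP), which was not available for this review.

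**The concern.** The four treatments do not carry the same risks, and Protocol 19.1 says so. Duloxetine has a long list of side effects, and suicidality on initiation is named as the most serious. MBSR has reported psychiatric worsening. Physical therapy has soreness, back pain and fatigue, rated occasional with seriousness 2. Acupressure had six related events in a trial of 288, all mild bruising. The safety population also includes entrants who are never randomised.

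A single pooled rate can therefore hide an excess in one treatment. If the pooled alarm does sound, the plan has no output that shows where the events came from. The trial is meant to learn which treatment suits which patient, so harm by treatment is part of the answer.

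**Working it through.** **1. The plan's own rule.** With four groups of 100, Fleming's upper limit is the nearest integer to n·p0 + 1.645·√(N·p0·(1−p0)), plus 1. With p0 = 0.10 and N = 400 the second term is 1.645 × 6 = 9.87. At n = 100, 200, 300 and 400 the limits are 21, 31, 41 and 51, the SAP's figures. The average sample number is 265.5 at a 10% rate and 252.4 at 15.4%, matching the SAP's 265 and 253. Read literally (looks at 102, 204, 306 and 408, and more than 21, 31, 41 and 51), an exact binomial recursion with no early acceptance gives an alarm probability of 5.0% at a pooled 10% and 91.9% at a pooled 15%. That literal rule is used below.

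**2. Inputs from the documents.**
- "Approximately 102 patients will be assigned to each treatment group" (SAP 5.1), so duloxetine is first treatment for 102/408 = 25% of those randomised.
- "it is expected that approximately 500 participants may be consented to meet enrollment" (SAP 5.4.1), so first-stage duloxetine is about 102/500 = 20% of the safety population.
- At T3, those with PGIC of 2 or more "will be re-randomized to receive one of the three treatments they did not receive in the first treatment period" (SAP 5.1). If all are re-randomised, 102 + 306/3 = 204 patients, or 50%, receive duloxetine at some point.

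**3. Inputs the documents do not give (assumptions).** These are the rate of related grade 2 or higher events under each treatment and the share s re-randomised. I take duloxetine at d = 20%, each other treatment at q = 2%, 3% or 5%, s from 0 to 100%, and events independent between stages.

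**4. Dilution in the first stage alone.** Pooled rate = 0.25d + 0.75q. For this to reach 15%, d must be (0.15 − 0.0375)/0.25 = 45% when q = 5%, or (0.15 − 0.015)/0.25 = 54% when q = 2%.

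**5. Alarm probability over both stages.** The proportion of patients with at least one event is

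p = (1 − s)(0.25d + 0.75q) + s·{0.5[1 − (1 − d)(1 − q)] + 0.5[1 − (1 − q)²]}.

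For d = 20%, q = 5%, s = 1: 0.5 × 0.24 + 0.5 × 0.0975 = 16.9%. Putting each p through the rule in step 1, with d = 20%:

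| Re-randomised | Others 2%: p, alarm | Others 3%: p, alarm | Others 5%: p, alarm |
|---|---|---|---|
| 0% | 6.5%, <0.1% | 7.3%, <0.1% | 8.8%, 0.6% |
| 50% | 9.6%, 3% | 10.7%, 12% | 12.8%, 56% |
| 85% | 11.8%, 33% | 13.1%, 63% | 15.7%, 96% |
| 100% | 12.8%, 55% | 14.2%, 82% | 16.9%, 99% |

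With d = 15% and s = 85-100%, the alarm fires 3-8% (others 2%), 14-30% (3%) or 70-87% (5%) of the time.

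**6. What a rate by treatment would offer.** With 102 first-stage duloxetine patients and a rate of 20%, the approximate 95% half-width is 1.96·√(0.2 × 0.8/102) = 7.8 percentage points. That is precise enough to be informative, and it shows where events arise whether or not the pooled alarm has fired.

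**The case against.** The pooled rule is not the only safeguard. Staff are not blinded (Protocol 8.2, SAP 5.5). The investigators classify the relatedness and severity of every event (Protocol 23.1.1). Duloxetine patients have scheduled calls and a post-treatment visit at which adverse events are documented (Protocol 9.4.1 to 9.4.3). All serious events reach NIAMS within 48 hours (Protocol 23.1.6). The DSMB is to see data from each arm, its charter is to define the data elements it needs, and the DSMP may already contain the tables. This stands, and it rules out three stronger readings.

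- A reader might infer that the trial will produce no adverse-event rate by treatment, or that a duloxetine excess would go unnoticed. The documents show only that the SAP specifies no such rate. Treatment received is known, so what is missing is pre-specification, not data.
- A reader might treat 15% as a limit that duloxetine must not exceed. It is the alarm level for the pooled rate; neither document sets a level for one treatment.
- A reader might call SAP 7.2.3 and Protocol 23.2.1 flatly contradictory. Both can be carried out as written: one defines the SAP's analysis, the other the board's review. They are not aligned, which is a lesser fault.

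The dilution can also be slight. With the other treatments at 5% and 85% or more re-randomised, the alarm fires at least 96% of the time for a 20% duloxetine rate. A 2% background is not supported for physical therapy, given the Protocol's own risk table. Nor is a look at one treatment always the better detector. With duloxetine at 15% and the others at 5%, an exact one-sided 95% lower bound above 10% among the roughly 190-200 patients ever exposed would be met 63-65% of the time, against 70-87% for the pooled alarm.

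None of this supplies the missing output. Board review does not commit the final report to rates by treatment, and the SAP, which governs the analysis, says treatment is to be disregarded.

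**Conclusion.** The point holds as a gap in the SAP. Its safety analysis disregards treatment by explicit rule, its one alarm is pooled, and it plans no adverse-event rate by treatment, while the Protocol assigns the DSMB a review of each arm and describes unlike risks.

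Dilution is possible, but the documents do not determine its size. Under assumed rates of 20% for duloxetine and 2-5% for the others, the alarm probability runs from under 1% with no second-stage exposure to 33-99% with 85-100% re-randomised. The range rests on those rates, the re-randomised share and independence between stages, none of which is in the documents. The lack of attribution once an alarm has fired does not depend on these assumptions. The change should be made; the primary endpoint is unaffected.

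**What to change.** Keep the pooled rule. Add to SAP section 10, for each safety look and for the final report, a table of related grade 2 or higher and serious adverse-event rates by treatment received, with exact confidence intervals and with stage 1 and stage 2 shown separately. Amend SAP 7.2.3 so that it no longer excludes analysis by treatment and is consistent with Protocol 23.2.1. If the DSMP already defines tables by arm, a cross-reference plus the final-report table is enough. No new stopping rule is proposed.

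The cost is about one extra table per report, from data already collected, and a few more comparisons for the board to read.
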